8.3.1.5. Relationship to Study Drug

Each AE must be assessed by the investigator, based on clinical judgment, as to whether or not there is a reasonable possibility of causal relationship to study drug and reported as either related or unrelated.

- A “reasonable possibility” of a relationship conveys that there are facts, evidence, and/or arguments to suggest a causal relationship, rather than a relationship cannot be ruled out.
- Alternative causes, such as underlying disease(s), concomitant therapy, and other risk factors, as well as the temporal relationship of the event to study drug administration will be considered and investigated.
- For each AE/SAE, the investigator must document in the medical notes that he/she has reviewed the AE/SAE and has provided an assessment of causality.
- There may be situations in which an SAE has occurred and the investigator has minimal information to include in the initial report to Cytokinetics. However, it is very important that the investigator always assesses causality for every event before the initial transmission of the SAE data to Cytokinetics.
- The investigator may change his/her opinion of causality considering follow-up information and send an SAE follow-up report with the updated causality assessment.

8.3.1.6. Relationship to Study Procedures

An AE is defined as related to study procedures if it appears to have a reasonable possibility of a causal relationship to protocol-required procedures.

8.3.1.7. Reporting of AEs

The investigator is responsible for ensuring that all adverse events observed by the investigator or reported by the patient that occur after starting the study drug through end of study are recorded in the AE CRF.

ALS is a progressive and uniformly fatal neurodegenerative disorder associated with relentlessly progressive loss of motor function, including appendicular, craniobulbar, and respiratory function due to the degeneration of the upper and lower motor neurons which control and innervate the voluntary skeletal muscles. The following conditions are anticipated to occur in the study population as signs/symptoms of ALS progression and do not need to be recorded as an AE unless they meet the criteria for an SAE, are felt to be related to the study drug, or they are occurring outside what is expected for the normal course of the disease ([Brown 2017](#)).

Table 4: Signs and Symptoms Commonly Associated with ALS

MedDRA Preferred Term ^a	MedDRA Preferred Term ^a
Dysarthria	Muscle spasticity
Dysphagia	Muscle contractions involuntary
Dyspnoea	Muscle spasms
Gait disturbance	Muscular weakness

^aMedDRA Version 23.0

8.3.1.8. Reporting Procedures for SAEs

Prompt notification by the investigator to Cytokinetics of an SAE is essential so that legal obligations and ethical responsibilities towards the safety of patients and the safety of an IP under clinical investigation are met.

The investigator is responsible for ensuring that all SAEs observed by the investigator or reported by the patient that occur after study drug initiation through end of study, or four weeks after the last administration of study drug, whichever is later, are recorded in the AE CRF and immediately reported to Cytokinetics on an SAE Report Form (no later than 12 hours following the investigator's knowledge of the event).

SAE Report forms must be emailed or faxed to Cytokinetics Drug Safety (contact details are provided on the SAE Report form):

Email: [contact]

[contact]

The investigator must attempt to establish a diagnosis of the event based on signs, symptoms, and/or other clinical information. Whenever possible, the diagnosis (not the individual signs/symptoms) will be documented as the AE/SAE.

The investigator must complete the SAE Report form in English and must assess the causal relationship of the event to study drug.

If the patient is hospitalized in a hospital other than the study site, it is the investigator's responsibility to contact this hospital to obtain all SAE relevant information and documentation.

New information relating to a previously reported SAE must be immediately reported to Cytokinetics (no later than 12 hours following knowledge of the new information). Cytokinetics Drug Safety may contact the investigator to obtain further information.

8.3.1.9. Follow-up of AEs and SAEs

The investigator is obligated to perform or arrange for the conduct of supplemental measurements and/or evaluations as medically indicated or as requested by Cytokinetics to elucidate the nature and/or causality of the AE or SAE as fully as possible. This may include additional laboratory tests or investigations, histopathological examinations, or consultation with other health care professionals.

If a patient dies during participation in the trial or during a recognized follow-up period, the investigator is encouraged to provide Cytokinetics with a copy of any post-mortem findings including histopathology if it has been performed.

Non-serious adverse events must be followed until they resolve or until the patient completes the trial, whichever comes first. Serious adverse events and adverse events of special interest still ongoing at the end of study must be followed up until resolution or stabilization, or until the event outcome is provided, eg, death. Reporting may continue after the follow-up visit and database lock.

New SAEs occurring after the 4-week follow-up period must be reported to the Cytokinetics Drug Safety department within 24 hours of the investigator's knowledge of the event, only if considered by the investigator to be causally related to previous exposure to the study drug.

8.3.1.10. Regulatory Reporting

The reference safety document to assess expectedness of a suspect serious adverse reaction and reported by Cytokinetics to Health Authorities, IRBs/IECs, and investigators is the reference safety information section of the IB for reldesemtiv.

Cytokinetics will report SAEs and/or suspected unexpected serious adverse reactions as required to regulatory authorities, investigators/institutions, and IRBs/IECs in compliance with all reporting requirements according to local regulations and good clinical practice.

The investigator is to notify the appropriate IRB/IEC of SAEs occurring at the site and other adverse event reports received from Cytokinetics, in accordance with local procedures and statutes.

8.3.1.11. Pregnancy and Breastfeeding

Female Patients Who Become Pregnant

If a female patient becomes pregnant while on study drug, study drug must be discontinued. The investigator must counsel the patient and discuss the risks of continuing with the pregnancy and the possible effects on the fetus.

Please refer to Appendix 3 ([Section 10.3](#)) regarding contraceptive guidance. Irrespective of the treatment received by the patient, any pregnancy occurring in a female patient, or female partner of a male patient, after study drug initiation up to 4 weeks following study drug discontinuation must be reported to Cytokinetics within 24 hours of the investigator's knowledge of the event.

Pregnancies must be recorded in the CRF and reported on the Cytokinetics Pregnancy Report Form, which is emailed or faxed to Cytokinetics Drug Safety (contact details are provided on the Pregnancy Report Form):

Email: [contact]

[contact]

Note: Sites are not required to provide any information on the Pregnancy Report Form that violates the country or region's local privacy laws.

Details of all pregnancies in female patients and female partners of male patients will be collected after the start of study drug and until the conclusion of the pregnancy. The follow-up of an infant (if applicable) will be conducted up to 12 months after the birth of the child.

Any pregnancy complication or elective termination of a pregnancy for medical reasons must be reported as an AE or SAE.

Abnormal pregnancy outcomes (eg, spontaneous abortion, fetal death, stillbirth, congenital anomalies, ectopic pregnancy) are considered SAEs.

A developmental delay of an infant, or suspected adverse reactions in a neonate will be reported as an adverse event or serious adverse event.

Any post-study pregnancy-related SAE considered reasonably related to study drug by the investigator will be reported to Cytokinetics as described in [Section 8](#). While the investigator is not obligated to actively seek this information in former study patients, he or she may learn of an SAE through spontaneous reporting.

Male Patients with Partners Who Become Pregnant

If a male subject fathers a child while on study drug, he may continue receiving treatment; however, he must use barrier method (ie, condom) during sexual intercourse to avoid further fetal exposure.

The investigator will attempt to collect pregnancy information on any male patient's female partner who becomes pregnant while the male patient is in this trial.

After obtaining the necessary signed ICF from the pregnant female partner directly, the investigator must complete the Pregnancy Report Form and submit it to Cytokinetics within 24 hours of receipt of the partner's consent. The female partner will also be followed to determine the outcome of the pregnancy. Information on the status of the mother and child will be forwarded to Cytokinetics.

Female Patients Who Breastfeed

If a female patient breastfeeds while on study drug, study drug will be discontinued.

The investigator will collect breastfeeding information on any female patient who breastfeeds while taking the study drug through 5 days after the end of study drug treatment. The mother and infant health information will be recorded on the Pregnancy Report Form and submitted to Cytokinetics immediately and no later than 24 hours following the investigator's knowledge of event.

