4.2. End of Study Definition

The end of the study is defined as the date of the last visit of the last patient in the trial.

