5.1. Inclusion Criteria

Patients are eligible to be included in the trial only if all the following criteria apply:

101. Able to comprehend and willing to sign an ICF and willing to comply with all study procedures and restrictions for the duration specified in the Schedule of Activities (SoA; [Section 1.3](#)). If patient is able to comprehend, but non-written consent is given, an impartial witness must sign the ICF form.
102. Completed dosing in CY 5031
103. Male patients, who have not had a vasectomy with medical assessment of surgical success, or a confirmed sperm count of zero, are eligible to participate if they agree to the following during the trial and for at least 10 weeks after the last dose of study drug:
 - a. Refrain from donating spermPlus when their female partner is of childbearing potential must either:
 - b. Be abstinent from heterosexual intercourse and agree to remain abstinentOR
Must agree to use a male condom AND have his female partner use a highly effective method of contraception (as described in Appendix 3 [[Section 10.3](#)])
104. A female patient is eligible to participate if she is not pregnant or breastfeeding, and at least one of the following conditions applies:
 - a. Is not a woman of childbearing potential (WOCBP; as described in Appendix 3 [[Section 10.3](#)])OR
Is a WOCBP and using a highly effective method of contraceptive (as described in Appendix 3 [[Section 10.3](#)]) and her male partner agrees to use a male condom during the trial and for at least 4 weeks after the last dose of study drug.
 - b. A WOCBP must have a negative pregnancy test (urine or serum as required by local regulations)

Note: The investigator is responsible for review of medical history, menstrual history, and recent sexual activity to decrease the risk for inclusion of a woman with an early undetected pregnancy.

Contraceptive use by men or WOCBPs should be consistent with the guidance in Appendix 3 ([Section 10.3](#)) and local regulations regarding the methods of contraception for those participating in clinical studies.

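### Once a man has left the trial, a partner pregnancy that begins about 5 to 10 weeks after his last dose has no clear reporting duty, although male precautions run for at least 10 weeks

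*Protocol*

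**What the plan says.** Three rules in the Protocol bear on this point.

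- **Reporting window (Section 8.3.1.11).** One sentence covers female patients and female partners of male patients. A pregnancy occurring "after study drug initiation up to 4 weeks following study drug discontinuation must be reported" to the sponsor. The limit applies to when the pregnancy occurs. The report itself is due 24 hours after the investigator learns of it, whenever that is.
- **Male-partner rule (same section, subsection on male patients).** The investigator tries to collect information on a "female partner who becomes pregnant while the male patient is in this trial". The pregnancy form follows once the partner has consented.
- **Male precautions (Section 5.1, criterion 103).** Men without a confirmed successful vasectomy or zero sperm count must not donate sperm. If the partner can become pregnant, they must also abstain, or use a condom while she uses highly effective contraception. This applies "during the trial and for at least 10 weeks after the last dose of study drug".

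Section 8.3.1.11 has two further sentences with no onset limit. One says that pregnancies go into the case report form and onto the sponsor's pregnancy form. The other says that pregnancy details, for patients and partners, are gathered from the start of dosing until the pregnancy ends.

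**The concern.** The protocol asks men to prevent a pregnancy for at least 10 weeks after the last dose, but clearly asks to be told of one only if it begins in the first 4 weeks or while the man is still in the trial. If a precaution fails after he has left, the pregnancy may be neither recorded nor followed to its outcome.

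The mismatch is on the male side. Criterion 104 sets a contraception period of at least 4 weeks after the last dose for women of childbearing potential, which equals the reporting window. One window appears to serve both groups, although the male precaution period is longer. The documents give no reason for the difference.

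What is at stake is the completeness of safety follow-up. No endpoint, sample size or planned analysis depends on it.

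**Working it through.** The plan states no figure for this gap, so there is none to reproduce. The check sets the time windows against each other.

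**Inputs**

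- Reporting window: 4 weeks = 28 days after discontinuation (Section 8.3.1.11). Discontinuation is taken as the last dose.
- Male precautions: at least 10 weeks, taken at the minimum of 70 days after the last dose (criterion 103).
- Last dosing day for a completer: Week 48 (Section 6.4), day 336 ± 4 (Section 8, Table 3).
- Last visit for a completer: Week 52, day 364 ± 4 (Table 3).
- Early stoppers: Section 7.2.1 lets a man agree to the early discontinuation visit only, or to remain in follow-up.

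**Formula.** Let E be the days from last dose to leaving the trial. The window sentence covers 28 days and the male-partner rule covers E days, so

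uncovered days = max(0, 70 − max(28, E)).

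Since max(28, E) is never below 28, the result cannot exceed 70 − 28 = 42 days.

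**Results**

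| Case | E (days) | Uncovered (days) |
|---|---|---|
| Completer, nominal dates | 364 − 336 = 28 | 70 − 28 = 42 |
| Completer, shortest interval within windows | 360 − 340 = 20 | 70 − 28 = 42 |
| Completer, longest interval within windows | 368 − 332 = 36 | 70 − 36 = 34 |
| Completer, dose at day 336, last visit 14 days after its nominal date | 42 | 70 − 42 = 28 |
| Early stopper leaving within 28 days of last dose | ≤ 28 | 42 |
| Any man leaving 70 days or more after last dose | ≥ 70 | 0 |

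For completers the in-window range is 34 to 42 days, if the last dose falls at the Week 48 visit. Section 8 allows visits outside the windows, so 34 is not a firm lower limit.

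At nominal dates the uncovered period is days 29 to 70, or Weeks 5 to 10, which is 42 of the 70 post-dose days. With the partner window at 70 days, the formula becomes max(0, 70 − max(70, E)) = 0 for every E.

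**Number of men affected.** This cannot be computed. About 400 patients are expected (Section 4.1), but sex, sterilisation status and partner status are not given.

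**The case against.** **Unlimited sentences.** The best counter-argument lies in Section 8.3.1.11 itself. The two sentences without an onset limit could set a general duty to record and report, leaving the 4-week sentence to govern only the 24-hour report. That reading is possible. The more natural one is that they give the procedure for pregnancies inside the window just defined. They do not say how a site would learn of a pregnancy after the man has gone. What stands is that the text is ambiguous, not plainly silent.

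**Onset, not detection.** A pregnancy that began in Week 3 and came to light in Week 8 is still reportable. It would be wrong to infer that all reporting stops at 4 weeks. Men who stop drug but remain in follow-up are covered for as long as they stay.

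**No rule requires the windows to match.** This is correct. Appendix 3 limits ova donation for 10 weeks, while the pregnancy window for women is 4. The case here is that a stated precaution should have a matching report. It makes no proposal about the female window.

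**Drug exposure.** A reader might infer that a pregnancy in Weeks 5 to 10 is drug-exposed. The documents give no rationale for the 10 weeks, so they do not support that.

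**SAE rules.** A reader might also infer a conflict in the handling of abnormal outcomes. Section 8.3.1.8 takes SAEs "through end of study, or four weeks after the last administration of study drug, whichever is later", whereas Section 8.3.1.9 takes new SAEs after the 4-week follow-up "only if considered by the investigator to be causally related to previous exposure to the study drug". Whether these collide depends on whether end of study in the reporting sections means the trial-wide date in Section 4.2. That is a general question about SAEs. It concerns outcomes rather than the pregnancy itself, and the change proposed here does not touch it, so no claim is made. Late pregnancy-related SAEs judged related to study drug are in any case reportable under Section 8.3.1.11: "Any post-study pregnancy-related SAE considered reasonably related to study drug by the investigator will be reported".

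**Practical value.** It is small. There is no scheduled contact after exit, and SAP Section 4.2 records that the study was terminated early.

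**Conclusion.** The point holds in a limited form. For a man subject to criterion 103 who has a partner of childbearing potential, has left the trial by about 4 weeks after his last dose, and is not continuing drug in the Managed Access Program, a partner pregnancy beginning in about Weeks 5 to 10 has no clear reporting duty. The gap is up to 42 days, less if he leaves later, and none if he leaves at 70 days or more.

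This rests on three assumptions: discontinuation means the last dose, 10 weeks is taken at its stated minimum, and being in the trial ends at the man's own last visit or contact. It is an inexpensive improvement to safety reporting and not the correction of an analysis error.

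**What to change.** 1. In Section 8.3.1.11, set the reporting window for female partners of male patients to pregnancies with onset up to at least 10 weeks after the last dose.
2. In the male-partner subsection, after the condition that the man is in the trial, add *or within 10 weeks after his last dose, whichever is later*.
3. At the Week 52 or early discontinuation visit, ask men with a partner of childbearing potential to tell the site of any such pregnancy.

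The mismatch should not be closed by shortening the precaution period.

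The cost is two phrases and one exit instruction. The downside is a few extra reports after exit, each depending on the man's notification and the partner's consent. Given the early termination, the change helps only men still within 10 weeks of their last dose, and any related protocol that uses the same wording.

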8.4. Treatment of Overdose

There is no established treatment for an overdose.

In the event of an overdose, the investigator should:

- Contact the Medical Monitor immediately who may recommend:
 - a. Close monitoring of the patient for any AEs/SAEs and laboratory abnormalities.
- Document the quantity of the excess dose as well as the duration of the overdose in the CRF.

Decisions regarding dose interruptions or modifications will be made by the investigator in consultation with the Medical Monitor based on the clinical evaluation of the patient.

8.5. Pharmacokinetics

No pharmacokinetic testing will be done for this trial.

8.6. Immunogenicity Assessments

No immunogenicity assessments will be done for this trial.

8.7. Sample Storage

The central laboratory will perform the standard safety testing described in this protocol. Any laboratory samples remaining after analysis may be temporarily stored for retesting and then will be destroyed. Laboratory samples will not be retained beyond the end of the study.

9. STATISTICAL CONSIDERATIONS

9.1. Populations for Analyses

The analysis populations are defined in [Table 5](#). Efficacy comparisons will be based on the data collected during CY 5031 from the patients in the full analysis set (FAS) of CY 5031 plus the data collected during CY 5032 from the patients who were in the FAS of CY 5031 and enrolled into CY 5032. Safety comparisons will be based on the data collected during CY 5032.

To minimize bias, the randomized treatment assignments in CY 5031 for those in the Safety Analysis Set in CY 5032 will be remained blinded to the site staff until the patients complete or terminate from the OLE.

Table 5: Analysis Sets

Analysis Set	Description
Full Analysis Set	All enrolled patients who received any amount of study drug and have a baseline and at least one post baseline efficacy assessment during CY 5031, regardless of the enrollment status in the OLE.
Safety Analysis Set	All enrolled patients who received any amount of study drug in the OLE.

9.2. Statistical Analyses

The Statistical Analysis Plan (SAP) will be finalized prior to database lock and it will include a more technical and detailed description of the statistical analyses described in this section. This section is a summary of the planned statistical analyses of the most important endpoints including primary and key secondary endpoints.

9.2.1. General Considerations

Summary tables will present descriptive statistics such as number of patients, mean, median, standard deviation, minimum and maximum for continuous variables, and number of patients and the percentage for categorical variables, overall and by early-start and delayed-start treatment groups in the planned analysis sets for all endpoints. For model-based analyses, least squares means, difference of least squares means between early-start and delayed-start treatment groups, their standard errors and 95% confidence intervals (CI), and two-sided p-values will be presented. For survival analyses, time to event will be summarized by median, 95% CIs of median, and 1st and 3rd quartiles. Events and censored data points will be summarized by count and percentage. Hazard ratios between the early-start and delayed-start treatment groups and the corresponding 95% CIs and p-values will also be presented. Analyses for comparisons will be conducted from baseline of CY 5031 through CY 5032 Week 48 and from Week 24 of CY 5031 through CY 5032 Week 48.

Comparisons between the delayed-start treatment group and the early-start treatment group will be presented using the nominal p-values at the two-sided 5% significance level.

Listings will include patient ID, demographics, treatment assigned and other relevant items, and sorted by treatment assignment, patient ID and date of assessment.

Unless specified otherwise, efficacy and safety analyses will be performed on the full analysis set and safety analysis set respectively. Statistical analysis methods will be detailed in the SAP.

